**Exclusion Criteria:**

1. The subject is pregnant or lactating.
2. The subject failed more than 2 adequate treatment with FDA-approved antidepressants during current episode per ATRQ criteria (less than 50% decrease in depressive symptomatology).
3. Structured psychotherapy focused on treating the subject’s depression (i.e. CBT or IPT) is permitted if started at least 8 weeks prior to the screening visit.
4. Substance dependence or abuse in the past 3 months.
5. History of a psychotic disorder or psychotic episode (current psychotic episode per MINI assessment).
6. Bipolar affective disorder (per MINI assessment).
7. Unstable medical illness, defined as any medical illness which is not well-controlled with standard-of-care medications (e.g., insulin for diabetes mellitus, HCTZ for hypertension).
8. Active suicidal or homicidal ideation (both intention and plan are present), as determined by C-SSRS screening.
9. Cognitive impairment (MOCA < 21)
10. The subject has a significant skin condition (i.e., hemangioma, scleroderma, psoriasis, rash, open wound or tattoo) on the subject’s scalp that is found to be in proximity to any of the procedure sites.
11. The subject has an implant of any kind in the head (e.g. stent, clipped aneurysm, embolised AVM, implantable shunt – Hakim valve).
12. Any use of light-activated drugs (photodynamic therapy) within 14 days prior to study enrollment (in US: Visudine (verteporfin) – for age related macular degeneration; Aminolevulinic Acid- for actinic keratoses; Photofrin (porfimer sodium) – for esophageal cancer, non-small cell lung cancer; Levulan Kerastick (aminolevulinic acid HCl) – for actinic keratosis; 5-aminolevulinic acid (ALA)- for non-melanoma skin cancer)
13. Recent history of stroke (90 days).

14. The subject failed a device-based intervention FDA-approved for the treatment of depression, during the current episode (e.g. less than 50% decrease in depressive symptomatology with TMS, ECT or VNS).

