### ***4.3 Study Population***

#### **4.3.1 Population Description**

The subject population for this study will consist of 50 subjects between the ages of 18 and 70, of any ethnic background and diagnosed with major depressive disorder. The subject will meet all the inclusion criteria, have none of the exclusion criteria, and provide their written Informed Consent to participate in this clinical study. Any subject who signs informed consent will be considered enrolled into the study, although they may not participate if they do not qualify for the study. In the event that a subject's ability to comprehend and communicate is compromised (per the assessment of the Investigator), local regulations pertaining to Informed Consent signatures should be followed.

Subjects will be recruited, via screenings, advertisements and postings. Study participants will also be recruited via internet-based advertisements, e.g., Craigslist, Clinical Trials @ Partners, the study sites websites, RSVP for Health (which will also generate listserv emails to Partners employees, regarding research studies in need of volunteers), etc.

Participants who contact the respective study site staff in response to any of the aforementioned advertisements will complete phone screening questions to determine tentative eligibility for the study.

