##### Screening Visit (Week -1)

The Principal Investigator (PI) at the site or a Sub-investigator will assess patients against the inclusion and exclusion criteria. If a patient appears to qualify and agrees to participate in the study, then the patient will undergo the informed consent process prior to initiation of any study-specific activities. Screening Case Report Forms (CRFs) will be completed and subjects who qualify to participate in the study will proceed to the first Treatment Visit 1. If the subject does not meet entry criteria, the Investigator will document the subject's ineligibility for study participation and complete the appropriate CRFs.

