###### Procedures

At this visit subjects will receive a psychiatric evaluation, will be consented for the study, and will be screened for presence of MDD using the MINI. The HAM-D-17, QIDS-C, SDQ and CGI will be used to assess severity of depressive symptoms, the ASQ will be used to assess anxiety symptoms, and the C-SSRS will be used to assess suicidality. The ATRQ will be used to assess resistance to treatment. The MoCA will help determining cognitive impairment that would contraindicate study participation.

Routine laboratory tests (including urine collection for Urine Analyses, Urine Tox Screen, and Urine Pregnancy Test) and complete physical exam including vitals and weight will be performed at screen; the tests will be processed by a laboratory at MGH and at NYUSOM.

About 15cc ± 5cc (15 mL) of blood is drawn for laboratory safety tests. To confirm a patient is healthy enough to participate a complete blood test with differentials, thyroid stimulating hormone test, a comprehensive 14-metabolic panel test, and a c-reactive high sensitivity protein test are conducted on screening day. An additional 2-6 cc of blood will be drawn for the cytokine assays during the screen visit.

Once all tests and procedures become available for review, the Investigator will then proceed to closely re-evaluate the subject for all the inclusion and exclusion criteria.

Subjects are allowed into the study if they did not fail more than two antidepressants in the current episode. Subjects could decide to continue their antidepressant during the study or to taper it off prior to the baseline visit.

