##### **4.8.2 Treatment Visits – Visits 1-24 (Weeks 1-12)**

The Treatment Sessions will occur twice weekly for twelve weeks at MGH Depression Clinical and Research Program (DCRP) in Boston and at NYUSOM Nathan S. Kline Institute (NKI), Orangeburg, NY. Subjects missing one session will be allowed to still receive their treatment within the same week. The study PI will be an active participant in the delivery of the TLT. The PI and other collaborators from MGH DCRP and at NYUSOM NKI will assist with the delivery of TLT. The device (TPBM-1000) for the

administration of the TLT will be provided by Litecure Inc. Litecure will provide training of MGH DCRP and NYUSOM NKI staff in the use of the device and will provide training certificates at the completion of the training.

The overall session is estimated to last about 25 min. Study sessions will take place in an office dedicated to TLT treatment at MGH DCRP and at NYUSOM NKI. Only the subject and the staff administering the TLT will be allowed during the session. The subject will comfortably lie down on an exam bed or sit on recliner. The sites of application of TLT (left and right forehead) will be inspected for any possible skin lesions (e.g. laceration or signs of inflammation) which would contraindicate the treatment. During treatment sessions the office will be kept completely dark and a warning sign will be hanged at the office door. The staff will be provided training on basic safety procedures relative to the use of the device.

The trained staff administering the TLT will use utmost care to never shine the light in or near the eyes of the subject safety goggles will be selected based on the TLT biophysical properties, in accordance to the Occupational Safety and Health Administration (OSHA) guidelines. The delivery of the TLT is expected to last 20 min total (simultaneous application on the left and right forehead). The subject will be asked to rest for five minutes after the delivery of TLT. The skin at the sites of the application will be inspected again prior to dismissing the subject. A log with the dates of treatment delivery per each study subject will be kept at MGH DCRP (Boston) and at NYUSOM NKI, NY.

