#### **4.17.2 Safety Monitoring**

The study subjects will undergo frequent clinical evaluations including depressive scores, concomitant medications, adverse events, and serious adverse events and unexpected device events will be recorded from study entry through completion. Additionally, doctors must monitor a subject's safety by asking the subjects frequently about the subject's own comfort during treatment application.

If skin erythema is present, treatment will be suspended. Patients will be instructed to contact the study site principal investigator or a member of his staff at any time between visits concerning adverse events or worsening of symptoms. If at any study visit the subjects' clinical condition is significantly worsened from baseline (operationalized as the clinical global impression severity score, CGI-S, of 6 or higher) or if a subject becomes actively suicidal with intent and/or plan, based on the C-SSRS scale and/or the clinical interview, the subject will be offered to start an antidepressant medication. If the subject were deemed at imminent danger as a result of suicidality, s/he would be discontinued from the study and referred to appropriate clinical treatment (see 4.8.4 Termination).

The two site Principal Investigators (Drs. [name] and [name]) will have bi-weekly conference calls (which will include study RAs); during these conference calls they will discuss all Adverse Event reports to identify any safety concern, based on such concerns they will be able to decide temporary discontinuation of study enrollment, modifications of the study protocol, or to terminate the study.

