## ***4.19 Subject Disposition Criteria***

### **4.19.1 Withdrawal from the Study**

Each subject and the Investigator reserve the right at any time to terminate a subject's participation in the clinical investigation.

Possible reasons for withdrawal or removal from the study may include:

1. The subject voluntarily withdraws consent.
2. The subject was not eligible based on the study inclusion and exclusion criteria.
3. The subject develops an Adverse Event that would not allow continuation in the study.
4. The subject has an Adverse Event which in the opinion of the Investigator warrants withdrawal from the study. Litecure Inc must be notified within two business days.
5. A decision is made by the subject and/or Investigator that the subject should be withdrawn from the study.
6. Subject death
7. Positive pregnancy test during the eligibility procedures

When a subject withdraws or is removed from the study, the following will be performed, if feasible, at the study termination (exit) visit:

- HAM-D-17
- QIDS-C
- CGI
- C-SSRS
- ADVERSE EVENTS FORM
- Concomitant medications form
- ASQ (self-rated)
- SAFTEE-SI (self-rated)
- SDQ (self-rated)
- NEURO-QOL (self-rated)
- SFI (self-rated),
- Cognitive tests

For all subjects who withdraw from the study prematurely, the date, and reason for withdrawal will be documented.

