### 6.3 *Monitoring Procedures*

Monitoring will be conducted by the PI who will periodically review lab results and clinical information. The PI will be coordinating the different phases of the protocol implementation such as TLT delivery and follow up. The PI will be frequently in contact with the other staff members responsible for TLT delivery and with Litecure Inc, which will lend the TLT device. We have minimized risks potentially associated with the use of Transcranial Light Therapy (TLT) by requiring two methods of contraception (although TLT has not been associated with teratogenic effect). In addition, we are providing the subjects with safety goggles or eye pads during the TLT delivery. We have also included treatment discontinuation rules based on the development of skin erythema, or discomfort

lasting more than 24 hours at the sites of TLT delivery (to prevent risk of subject's having an unknown skin photosensitivity).

Treatment will end for participants who experience temporary pain or discomfort during a treatment session. A research assistant or the study doctor will follow-up within a 24-hour period, after the discontinued treatment, with the patient who experienced discomfort. The subject may continue with the study if the acute pain stopped. If the subject experiences discomfort after 24-hours the aforementioned treatment discontinuation process may begin (e.g., Section 4.19.1, p. 29).

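### Exclusion 12 restricts light-activated drugs only in the 14 days before enrollment; no rule in the protocol bars them during the 12 weeks of light sessions

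*Protocol*

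**What the plan says.** Item 12 of the Exclusion Criteria (protocol, Study Summary) excludes "Any use of light-activated drugs (photodynamic therapy) within 14 days prior to study enrollment" and lists the drugs meant.

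Section 4.3.1 states: "Any subject who signs informed consent will be considered enrolled into the study". Section 4.7 places consent at the Screening Visit, headed Week -1, where "the patient will undergo the informed consent process prior to initiation of any study-specific activities". Once screening results are in, section 4.8.1 has the investigator "closely re-evaluate the subject for all the inclusion and exclusion criteria". Inclusion item 6 and the note in section 6.4 instead put consent before enrollment, without saying when enrollment then happens.

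Randomisation and the first session are at Visit 1 (4.8.2.1). Two sessions a week follow for 12 weeks (4.7).

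Several safeguards apply during treatment:
- Only physicians deliver the sessions (4.2).
- The skin is checked before each session for lesions that would rule treatment out, and afterwards: "The skin at the sites of the application will be inspected again prior to dismissing the subject" (4.8.2).
- "If skin erythema is present, treatment will be suspended" (4.17.2).
- Section 6.3 stops treatment for erythema or for discomfort beyond 24 hours, and gives as its reason the risk of a subject "having an unknown skin photosensitivity". A session also ends if it causes pain.
- Eye protection is worn (4.20.1).
- Item 5 of section 4.19.1 allows withdrawal when "A decision is made by the subject and/or Investigator that the subject should be withdrawn from the study".
- A concomitant-medication form is kept. Section 4.9 has it at every treatment visit; section 4.8.2.3 and Attachment 1 have it at odd-numbered treatment visits only.

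The SAP does not touch this point.

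**The concern.** An exclusion for recent use of a light-activated drug makes sense only in relation to light. Item 12 counts its 14 days back from enrollment, and no light is given before Visit 1. The period in which light is given carries no restriction at all. A subject could start a listed drug in week 3, follow every written rule, and have the next session a day or two later. The form might record the drug, but no action is attached to the entry. Starting such a drug is neither a listed reason for withdrawal (4.19.1) nor a trigger under Termination (4.8.4).

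The protocol does carry one entry condition forward: skin problems at the treatment sites are excluded by item 10 and looked for again at each session. Item 12 has no such counterpart. What is at stake is the safety of individual subjects; sample size, endpoints and analysis do not depend on the wording of this item.

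**Working it through.** The documents give no figure for this point, so there is none to reproduce. The check has two parts.

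**Which period does the rule cover?**
- Enrollment read as consent (4.3.1): the rule covers the 14 days before the Screening Visit. The interval to Visit 1 and all sessions are uncovered.
- Enrollment read as a later step, at latest Visit 1 (inclusion item 6, section 6.4): the interval to Visit 1 closes. The treatment weeks stay uncovered.
- The re-check of criteria in 4.8.1 applies the same item with the same window, so it does not extend the cover under either reading.

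**How long is the gap, and how many sessions could fall in it?**

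Inputs: Visit 1 = day 0; two sessions a week (4.7), taken as day 0 and day 3-4 of each week, which is an assumption about spacing. Visit 24 is then at 11 × 7 + 3.5 = day 80.5. Consent is at day -7 (Week -1). The protocol sets no maximum interval, so day -14 to day -1 is taken as an assumed range.

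- Gap from consent to Visit 24: 80.5 + 7 = 87.5, about 88 days. Range: 80.5 + 1 = 81.5 to 80.5 + 14 = 94.5 days.
- Gap if enrollment is Visit 1: 80.5 days.

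Now take a single use on day d and count light sessions from day d up to, but not including, day d + 14. This applies the protocol's own 14-day interval forwards.

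Active light from the start:
- Use the day after consent (day -6): sessions on days 0, 3-4 and 7, so 3. With consent on day -14 and use on day -13: day 0 only, so 1. With consent on day -1 and use on day 0: days 0, 3-4, 7 and 10-11, so 4. These pre-treatment cases matter only under the consent reading.
- Use in weeks 1-10: 2 weeks × 2 sessions = 4.

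Sham, then re-randomised to light (first light on day 42):
- Use on days 0-27 (weeks 1-4): 0.
- Weeks 5-6 (days 28-41): day 28 gives 0, day 29 gives 1, day 35 gives 2, day 38 gives 3 and day 41 gives 4. The range is 0-4.
- Use in weeks 7-10: 4.

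Sham throughout: 0.

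The most light sessions a subject can receive are 24, 12 and 0 in these three groups. With 1:2 allocation, subjects starting on light number 8 of 24 in PART-1 (5.3) and 26/3 = 8.7 of 26 in PART-2, so 16.7 of 50 in all. They carry most of the possible exposure.

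These counts describe what the written rules permit. They are not risks: the documents give no rate at which subjects might use a listed drug.

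**The case against.** The best case for leaving the text alone is that a physician delivers every session, inspects the skin first, sees a medication form and may withdraw the subject at any time. The pre-session skin check is truly preventive where inflammation is visible at the site. Entry criteria on unstable illness (item 7) and scalp skin conditions (item 10) plausibly shrink the number of subjects who would need a listed drug. All of this stands and makes the event less likely. It does not supply a rule. The skin check would miss a systemic drug that leaves no skin sign, the stop rules act after a reaction, and the discretion to withdraw names no drug.

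A second objection concerns hazard. The documents do not show that 830 nm light at this dose activates a listed drug, and they put device output below the permitted skin exposure (3.1, 4.20.1). A reader might infer from the gap that subjects face a demonstrated phototoxic risk. The documents do not support that. What they support is narrower: the protocol treats recent use as incompatible with entry, and does not apply that judgement while light is given.

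A reader might also infer that the week before Visit 1 is certainly uncovered. That follows from section 4.3.1, but inclusion item 6 and section 6.4 use enrollment for something after consent, so it is conditional on the reading. Finally, the consent form was not available for this review. It may contain medication instructions to subjects; that cannot be settled either way.

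**Conclusion.** The gap during treatment is real under either reading of enrollment: no rule bars a listed drug between Visit 1 and Visit 24. The gap before Visit 1, nominally one week, depends on enrollment meaning consent. Existing safeguards reduce the exposure without closing it.

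The size is small. At most about 4 light sessions would fall within 14 days of a single use, and such use is probably rare. That last statement is a judgement, since no rate is given. The session counts rest on evenly spaced twice-weekly sessions. The change is worth making because the present rule protects a period without light and leaves the period with light open, at almost no cost to correct. It is not a reason to doubt the trial's power, endpoints or analysis.

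**What to change.** Restate Exclusion 12 as no use of a listed light-activated drug within 14 days before Visit 1, and none through Visit 24. This also removes the dependence on what enrollment means.

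Check it on the existing concomitant-medication form, before treatment at each session. Section 4.9 already has the form at every treatment visit but does not say it comes before treatment; section 4.8.2.3 asks for it before treatment but only at odd-numbered visits. Align these and Attachment 1. The addition is a short medication question at 24 − 12 = 12 even-numbered sessions.

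Add one action rule: after any use, withhold sessions for 14 days, or withdraw the subject from treatment under 4.19.1. Apply it identically to light and sham, because withholding only active sessions would reveal the assignment. Keep the subject in scheduled assessments, as section 4.8.4 already encourages after treatment is discontinued.

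The cost is an occasional screen failure or hold. A 14-day hold loses about 4 sessions: 4/24 = 17% of the course, or 4/12 = 33% if it falls within one 6-week phase. Same-week rescheduling (4.8.2) would not recover most of them. With only 8 subjects on active light in phase 1 of PART-1, a hold there could slightly dilute the comparison. Since holds should be rare, that is an acceptable price.

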## List of Abbreviations

31P-MRS = Phosphorous-31 Magnetic Resonance Spectroscopy  
 ALA = 5-aminolevulinic acid  
 ASQ = Anxiety Symptoms Questionnaire  
 ATP = adenosine triphosphate  
 AVM = Arteriovenous Malformation  
 CADSS= Clinician Administered Dissociative States Scale  
 C-SSRS = Columbia-Suicide Severity Rating Scale  
 CFR = Code of Federal Regulations  
 CGI-I = Clinical Global Impressions - Improvement  
 CGI-S = Clinical Global Impressions – Severity  
 CHRT = Concise Health Risk Tracking  
 DCRP = Depression Clinical and Research Program  
 DNA = deoxyribonucleic acid  
 ECT= Electroconvulsive Therapy  
 FDA = Food and Drug Administration  
 HAM-D-17 = Hamilton Depression rating scale  
 ISO = International Standards Organization  
 MADRS = Montgomery-Asberg Depression Rating Scale  
 MOCA Montreal Cognitive Assessment  
 MDD = Major Depressive Disorder  
 MGH = Massachusetts General Hospital  
 NEST 1 = NEST 1 - NTS® Effectiveness and Safety Trial – 1  
 NEST 2 = NEST 2 - NTS® Effectiveness and Safety Trial – 2  
 NEURO-QOL = Quality of Life in Neurological Disorders  
 TSRQ = TLT Self-Report Questionnaire  
 NKI = Nathan S. Kline Institute for Psychiatric Research  
 NSMHA = North Suffolk Mental Health Associate  
 NYUSOM = New York University School of Medicine  
 OSHA = Occupational Safety and Health Administration  
 PBQ = Perceptions of Blinding Questionnaire  
 PCL-S = PTSD Checklist-Specific  
 PI = Principal Investigator at the site  
 QIDS-CR = Quick Inventory of Depressive Symptomatology-Clinician Rated Scale  
 SAE = Serious Adverse Event  
 SAFTEE-SI = Systemic Assessment for Treatment Emergent Events  
 SCID = Structured Clinical Interview for Diagnostic Statistical Manual-IV  
 SSRI = selective serotonin reuptake inhibitor

TLT = Transcranial Light Therapy  
TMS = Transcranial Magnetic Stimulation  
TS-1 = Treatment Sequence 1  
TS-2 = Treatment Sequence 2  
VNS= Vagus Nerve Stimulation

## 1. Introduction

Major Depressive Disorder (MDD) is a prevalent and disabling condition: 16.2 % of the US population has MDD at some point in life (Kessler et al., 2003). In the US, depression is the third leading cause of years lost because of disability or death, after cardiovascular diseases and lung and breast cancers (Michaud et al., 2006). Despite the availability of effective treatments such as antidepressants and psychotherapy, MDD frequently remains untreated, with only one fifth of the cases receiving adequate treatment (Kessler et al., 2003). Moreover, diagnostic and treatment rates for depression among Blacks and Hispanics are less than half the observed rates for Whites (Sclar et al., 2008). Hispanics and Blacks have significantly more concerns regarding the quality-of-life effects of medications than Whites (Huang et al., 2009). Among Hispanics stigma associated with receiving antidepressants is a prominent concern (Interian et al., 2007). Delayed treatment for depression, not only prolongs the associated disability, but might result in lower rates of response to antidepressants (de Diego-Adelino et al., 2009).

Current standard treatments for MDD are antidepressants and psychotherapy. Antidepressants are effective but their efficacy is often limited by adherence to treatment (Lingam and Scott, 2002). Psychosocial interventions are usually preferred in primary care (Backenstrass et al., 2006), especially among minorities (Givens et al., 2007), but they are typically not cost-effective due to the higher initial costs of providing psychotherapy (Barrett et al., 2005). In addition, counseling and psychotherapy are limited in the community by the lack of counselors who are culturally trained and proficient with specific languages (e.g. Spanish).

Because of the limitations of medication treatment and talk-therapy in the approach to depression, new treatment approaches are required especially in primary care and in the community, where several minorities are underserved. We propose a novel treatment approach for depression based on the use of the continuous and pulsed Transcranial Light Therapy (TLT). The treatment consists in exposing bilaterally the frontal brain to the TLT, which may enhance ATP production in depressed subjects.

Major Depressive Disorder has been associated with deficits in brain bioenergetic metabolism. In an experimental model of depression, the mitochondrial respiratory chain (the cellular site for energy production) was found to be inhibited by chronic stress (Rezin et al., 2008). Depressed subjects have also significantly lower production of ATP (an energy vector) in their muscle tissue and greater incidence of deletions in their mitochondrial DNA (Gardner et al., 2003). Data from magnetic resonance spectroscopy in subjects with MDD showed that response to the augmentation of a selective serotonin

reuptake inhibitor (SSRI) with triiodothyronine (a thyroid hormone) is associated with restoration of the levels of ATP in the brain ([name] et al., 2008).

The TLT is a non-ionizing electromagnetic wave. The TLT is invisible, penetrates the skin and skull into brain tissue, is non-invasive (Zhang et al., 2000), is minimally dissipated as thermal energy and is mainly absorbed by specific chromophores (Mochizuki-Oda et al., 2002). The benefits of TLT are wavelength specific. A mitochondrial enzyme, the Cytochrome c oxidase, is the primary chromophore for the TLT with wavelength around 830 nm (Eells et al., 2003). The energy absorbed by the cytochrome c oxidase leads to increased adenosine triphosphate (ATP) production, through the respiratory chain. Ultimately, the increased ATP leads to increased energy metabolism for the cell, and it is hypothesized that a signaling cascade is also activated promoting cellular plasticity and cytoprotection (Eells et al., 2003).

These properties of the TLT have led to novel therapeutic applications in neurology. In acute ischemic stroke subjects, acute treatment with the TLT led to significantly better outcome as compared to sham (Lampl et al., 2007). These results were confirmed in a different cohort of stroke patients with mild to moderate severity of illness (Zivin et al., 2009). Both studies on stroke subjects showed no significant difference in rate of adverse events, as well as serious adverse events, between the TLT and sham treated subjects (Lampl et al., 2007; Zivin et al., 2009) [See section 4.17]. The TLT has also been used as a treatment of alopecia (Leavitt et al., 2009) and in animal models for methanol-induced retinal toxicity (Eells et al., 2003). The near-infrared light is already widely used for non-invasive assessment of brain function (replacing fMRI in studies of infants and young adults, under the name of Near Infrared Spectroscopy) underscoring the relatively low risk of TLT. The major risk of TLT when using a laser as the light source is associated with accidental retinal exposure, when beams are projected through the lens, with increased risk of macular lesions (Kim et al., 2007). In our study, we will have multiple protections to safeguard against this risk [See section 4.17].

Preliminary uncontrolled studies in 10 and 4 depressed subjects, respectively, have shown that the TLT is safe, effective and well tolerated (Schiffer et al., 2009; [name] et al., 2015). Our study offers a larger sample size, a cleaner design with placebo-control (also called Sham treatment), and tests the efficacy and tolerability of repeated sessions of TLT. Because the TLT is a non-ionizing radiation, multiple sessions, likely required for the treatment of depression, are expected to be safe.

The advantage of the TLT treatment approach as compared to pharmacotherapy is that adherence can be easily monitored (since treatment is delivered at the clinic) and the patient is not required to ingest any substance. It is possible that the exposure to TLT might be more acceptable than use of medications among some minorities. As compared to talk-therapy, the TLT therapy has the advantage of not requiring providers with specific cultural expertise or second language proficiency. Our study will contribute to answer the question of whether TLT has an antidepressant effect and whether it is acceptable in minority populations, thus justifying further studies and investments.

